3.0 Investigational Plan

.1 Study design:

Randomized controlled double-blinded study

.2 Methods:

Size of study groups(s):

The primary outcome is the proportion of subjects in each group that have breakthrough pain requiring a manual bolus (redose) by the anesthesiologist. In previous studies that have used timed-intermittent boluses for maintenance of

labor analgesia, the percentage of patients that have required supplemental manual boluses of local anesthetic has ranged between 30-50%. We hypothesize that patients randomized to the rate of 300 mL/h will be less likely to require a supplemental manual bolus than those in the 100 mL/h group.^{1,7} Assuming that 50% of the patients in the 100 mL/h group will require supplemental manual boluses and 30% of patients in the 300 mL/hr group will required supplemental manual boluses, using a power of 0.8, and an alpha of 0.05Due to the dynamic nature of the labor and delivery floor in patients' clinical course and resultant decisions regarding their choices on pain control during labor there is a greater degree of unpredictability of enrolled patients being excluded from this study for both clinical and personal reasons. As a result 300 patients meeting inclusion criteria will be recruited to account for dropout and still maintain the ability to recruit the estimated 106 patients per study group.

Secondary outcomes are the total number of requested and delivered PCEA boluses, and bupivacaine consumption per hour of labor analgesia.

.2.1 Participant entry, exclusion and dropout criteria:

Inclusion criteria:

Nulliparous parturients who presents to the labor and delivery unit for an induction of labor or who are in spontaneous labor, and request neuraxial labor analgesia at < or = to 5cm cervical dilation are eligible to participate.

Exclusion criteria:

Patients who are not eligible to receive a combined spinal epidural (CSE) technique with 25 mcg of intrathecal fentanyl, non-English speaking, who experience failed CSE analgesia, need to have the epidural catheter replaced during labor, or who deliver within 90 minutes of initiation of labor analgesia will be excluded from the study.

.2.2 Protocol specific methods:

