Parturients who meet the inclusion criteria will be approached by one of the investigators, or one of the anesthesiology research nurses, for study participation. Parturients who are willing to participate in the study will provide written consent. Patient demographics will be collected at study enrollment.

Cervical dilation will be confirmed by a member of the obstetric team prior to epidural catheter placement as is routinely done at our institution. A baseline pain visual analog scale (VAS) score will be obtained using a 100-mm unmarked line with the end points labeled "no pain" and "worst pain imaginable."

Labor analgesia will be initiated using CSE analgesia with 25 mcg of intrathecal fentanyl. An epidural test dose will be performed as routine (1.5% lidocaine with epinephrine 1:200, 3 mL).

Labor analgesia will be maintained using timed-intermittent boluses of local anesthetic with PCEA using the CADD-Solis pump (Smiths Medical). An unblinded anesthesia research nurse will program the epidural pump and initiate the maintenance of labor analgesia.

The maintenance epidural solution for both groups will be bupivacaine 0.625 mg/mL with fentanyl 1.95 mcg/mL. The intermittent bolus volume will be 10 mL administered every 60 minutes. The first bolus will be given 30 minutes after intrathecal injection, as has been done in previous studies at our institution.⁷ The bolus rate will be 300 mL/h (2 minute 10 ml bolus infusion) in the high-rate bolus group, and 100 mL/h (6 minute 10 ml bolus infusion). In addition to the programmed boluses patients will be able to administer patient-controlled epidural analgesia (PCEA) boluses of 5 mL every 10 minutes to a maximum of 15 mL (three PCEA boluses in a one hour period).

The patient, anesthesiologist, and research nurse recording clinical data will be blinded to group assignment.

Fifteen minutes following the intrathecal dose, a VAS score and a sensory level of analgesia will be obtained. The following information will be obtained hourly until complete cervical dilation (10 cm): VAS pain score, sensory level, a modified Bromage score (0 - no motor paralysis; 1 - inability to raise extended leg, but able to move knee and foot; 2 - inability to raise extended leg and to move knee, but able to move foot; 3 - inability to raise extended leg or to move knee and foot).

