The subjects' identity will be guarded by assigning a numerical code which is only known by the principal investigator. Data is stored in a department computer which is password protected. Each study subject will be assigned a study code number. The code will be used to link study data to patient identification (name) in a separate database. Subject data will be stored on secured computers at Northwestern University. Data access will be password protected and only available to study investigators. The data forms will be de-identified after the chart review prior to analysis. 5 years after manuscript the data both electronic and paper will be destroyed using the current departmental standards.

5.0 Data Analysis:

- .1 Data collection form:** Data collection forms will include all of the information outlined above in study methods.

.2 **Data evaluation:** The primary outcome will be the proportion of patients requiring supplemental manual boluses of local anesthetic. Secondary outcomes are the total number of requested and delivered PCEA boluses, and bupivacaine consumption per hour of labor analgesia. In addition, time to first PCEA request, time to first supplemental manual bolus, and motor block at 10 cm cervical dilation will be evaluated. Categorical data between groups will be compared using a chi-squared or Fisher's exact test, and continuous data will be compared using a two-tailed t-test or Mann Whitney U test as appropriate. Time outcomes will be compared between groups using a Kaplan–Meier survival analysis technique with log rank test. Patients undergo a cesarean delivery or do not request supplemental analgesia will be censored at the time of delivery. Labor pain will be calculated using the area under the VAS-time curve using the trapezium rule.

1.0 Labor Requirements: All labor will be performed by study investigators and the anesthesiology research nurses.

2.0 Consent: Please see attached consent form for this study.

.1 **Additional information for preparation of an IRB Submission:** N/A

References:

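### Every planned comparison is unadjusted, although labor type, cervical dilation and baseline VAS are known before the assigned bolus rates start; pre-specified adjustment could add precision at almost no cost.

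*Combined protocol and SAP*

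**What the plan says.** Section 5.0, Data evaluation, defines the endpoint: "The primary outcome will be the proportion of patients requiring supplemental manual boluses of local anesthetic". It then names a method for each type of data:

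- Categorical: "Categorical data between groups will be compared using a chi-squared" or Fisher's exact test.
- Continuous: "continuous data will be compared using a two-tailed t-test or Mann Whitney U test as appropriate".
- Time outcomes: a Kaplan–Meier "survival analysis technique with log rank test".

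No covariate, regression model, stratified test or stratified randomization appears anywhere in the document.

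Three baseline variables are available:

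- **Labor type.** The inclusion criteria in section 3.0 admit women who present "for an induction of labor or who are in spontaneous labor".
- **Cervical dilation.** Protocol specific methods: "Cervical dilation will be confirmed by a member of the obstetric team prior to epidural catheter placement".
- **Baseline pain.** Same section: "A baseline pain visual analog scale (VAS) score will be obtained using a 100-mm unmarked line".

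The first bolus at the assigned rate comes 30 minutes after the intrathecal injection, so the bolus rate cannot affect any of the three. On recording, section 5.0 says: "Data collection forms will include all of the information outlined above in study methods".

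**The concern.** When a baseline variable predicts the outcome, part of the variation between women can be explained before the arms are compared. An unadjusted comparison leaves that part in the standard error. Adjustment gives a narrower confidence interval and more power with the same women. When the variable predicts nothing, adjustment costs very little.

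The choice has to be written down before the data are seen. If an adjusted analysis is added afterwards, the covariates could have been picked because they favored one result, and a reader cannot rule that out.

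The trial plans to recruit 300 women to keep 212, which implies an allowance for loss of 1 − 212/300 = 29%. If fewer than 106 per arm remain, spare precision matters more. This is most so under Fisher's test, whose margin over 80% power is under two points.

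**Working it through.** **Inputs from the plan (section 3.0, size of study groups).** 50% in the 100 mL/h arm, 30% in the 300 mL/h arm, power 0.80, alpha 0.05, 106 per arm. Sidedness is not stated for the sample size; two-sided is assumed.

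**Step 1: the plan's own figure.** With mean proportion 0.40:

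n = [1.960 × √(2 × 0.40 × 0.60) + 0.842 × √(0.50 × 0.50 + 0.30 × 0.70)]² / 0.20² = 93 per arm.

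The continuity correction gives (93/4) × [1 + √(1 + 4/(93 × 0.20))]² = 103. Exact Fisher power first reaches 0.80 at 102 per arm. The stated 106 is within 3% of 103, so it reproduces.

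**Step 2: power as planned.** Exact enumeration at 106 per arm gives 0.850 for the uncorrected chi-squared test and 0.816 for Fisher. Both exceed 0.80.

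**Step 3: effect of adjustment, by formula.** If the covariates explain a share R² of the outcome variance, the variance of the risk difference is multiplied by (1 − R²), and the effective size per arm is 106/(1 − R²). Unadjusted, SE = √[(0.25 + 0.21)/106] = 0.0659, so the 95% half-width is 1.96 × 0.0659 = 12.9 percentage points. R² is assumed.

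| Assumed R² | Effective n per arm | Half-width (points) | Power |
|---|---|---|---|
| 0 | 106 | 12.9 | 0.849 |
| 0.02 | 108 | 12.8 | 0.857 |
| 0.05 | 112 | 12.6 | 0.867 |
| 0.10 | 118 | 12.3 | 0.885 |
| 0.20 | 133 | 11.6 | 0.918 |

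**Step 4: effect of adjustment, by simulation.** 10,000 trials per setting, 106 per arm, with marginal proportions held at 50% and 30%. Assumed covariates: labor type split 50/50, dilation uniform on 1–5 cm, VAS normal with mean 65 and SD 20 cut to 0–100, with equal standardised weights. The adjusted analysis is a logistic regression on arm and the three covariates, turned into a standardised risk difference with an influence-function standard error. The last column is 212 divided by the variance ratio.

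| Joint log-odds SD | c-statistic | Chi-squared power | Adjusted power | Variance ratio | Equivalent total n |
|---|---|---|---|---|---|
| 0 | 0.50 | 0.852 | 0.854 | 1.011 | 210 |
| 0.25 | 0.57 | 0.849 | 0.855 | 1.000 | 212 |
| 0.5 | 0.64 | 0.847 | 0.868 | 0.959 | 221 |
| 0.8 | 0.70 | 0.847 | 0.889 | 0.892 | 238 |
| 1.0 | 0.74 | 0.848 | 0.906 | 0.846 | 251 |

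Power differences of a few tenths of a point, as in the first two rows, should not be read as gains: the variance ratio there is 1.00 or above.

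**Step 5: type I error.** With 40% in both arms and SD 0, 0.5 and 1.0, the adjusted analysis rejects in 0.052, 0.051 and 0.051 of trials, and chi-squared in 0.049, 0.051 and 0.048. Smaller repeat runs gave 0.050 to 0.059 for the adjusted analysis, with Monte Carlo error of about 0.004. That is close to nominal.

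**Step 6: pain scores, a separate matter.** ANCOVA on baseline VAS reduces variance by r². An assumed correlation of 0.3 to 0.5 gives 0.3² = 9% to 0.5² = 25%.

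**The case against.** The strongest reply is that nothing is broken. The trial was sized on a difference in proportions, chi-squared tests exactly that contrast, and it has enough power. All of this stands, and it is why the point ranks as an optional improvement.

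The benefit also rests wholly on assumed prognostic strength, and the upper settings are demanding. With three independent, equally weighted covariates, a joint SD of 1.0 gives each a log-odds SD of 1/√3 = 0.577. A 50/50 binary variable has SD 0.5, so labor type would need an odds ratio of exp(0.577/0.5) = 3.2, while VAS and dilation would each need exp(0.577) = 1.8 per SD. Even at 0.8, labor type needs about 2.5. The women are already alike: nulliparous, at 5 cm or less, with the same initial block. The 4- and 6-point gains are therefore not what to expect by default. The simulation is also favorable, because it has complete covariates and fits the model that generated the data.

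Two narrower objections stand too. No sentence says outright that labor type is a field on the form. The additions for time outcomes and pain lack support from the documents. No gain was computed for a Cox model, whose adjusted hazard ratio is a conditional quantity. The pain correlation is assumed, and an area under the curve not divided by time also varies with the length of labor.

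None of this removes the case for the primary outcome. The possible loss is about 1% of variance, the possible gain is larger, and the standardised risk difference keeps the quantity the trial was powered on.

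**Conclusion.** The point holds as a low-priority improvement. All named comparisons are unadjusted, and three baseline variables are fixed before the assigned rates can act. Adjustment would give no real gain if the joint log-odds SD is 0.25 or less, and about 2, 4 or 6 points of power at 0.5, 0.8 or 1.0. The effective total size then runs from about 210 to 251 women against the planned 212.

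These figures rest on the plan's 50% and 30%, on 106 per arm with complete covariates, and on assumed covariate distributions and prognostic strength. Confidence in the size of the gain is moderate at best, because the documents do not show that any of the three predicts a manual bolus. That the unadjusted test is valid and adequately powered is not in dispute.

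**What to change.** In section 5.0, Data evaluation, name one primary analysis. The proportion needing a manual bolus is analysed by logistic regression with pre-specified terms for arm, spontaneous versus induced labor, cervical dilation at request and baseline VAS. It is reported as a standardised risk difference with a 95% confidence interval, because an adjusted odds ratio would be a different quantity from the powered difference in proportions. Keep the chi-squared or Fisher test as supportive. State in advance how dilation and VAS enter the model and how a missing baseline value is handled.

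Confirm that labor type, and dilation as found by the obstetric team, are fields on the data form.

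Optional additions, whose benefit cannot be sized from the documents: a Cox model with the same terms beside the log-rank test, and ANCOVA on baseline VAS for the VAS area under the curve.

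The cost is a few sentences, slightly more analysis work, and about 1% more variance if the covariates turn out not to be prognostic. No extra patients or visits are needed.

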Proposed Research Protocol Form
Northwestern University Feinberg School of Medicine

Title: Association between bolus rate and the adequacy of labor analgesia using timed-intermittent boluses for maintenance of labor analgesia

Principal Investigator: [name].

Co-investigator (s): [name], MPH,

Affiliation: Department of Anesthesiology, Northwestern University Feinberg School of Medicine

1.0 Research Aims:

Aim 1: To evaluate the association between bolus rate and duration of adequate labor analgesia.

Hypothesis: Patients whose labor analgesia is maintained using timed intermittent boluses with a high-rate bolus (300 mL/h) will have a longer duration of adequate analgesia (time to first manual redose request) than patients whose timed bolus is delivered with a lower-rate bolus (100 mL/h).

2.0 Research significance:

Background:

Neuraxial labor analgesia is usually maintained by the intermittent or continuous injection of local anesthetic combined with opioid through a catheter sited in the lumbar epidural space. Pain from the first stage of labor is primarily due to lower uterine segment and cervical stretching. The pain signals enter the spinal cord through sensory nerves at the T10 through L1 dermatomes. Pain signals from the late first state and second stage of labor also arise from the vaginal and perineum. These signals travel with the pudendal nerve and enter the spinal cord at S2-S4. Thus, the anesthetic solution administered through the lumbar epidural catheter must spread cephalad in the epidural space to reach the T10 nerve roots and spinal cord, and must spread caudad to reach the caudal nerve roots in the epidural space.

Administration of anesthetic solution into the epidural space is usually accomplished by a combination of continuous infusion, provider-administered boluses and patient-administered boluses (patient controlled epidural analgesia [PCEA]). The optimal method for maintaining labor analgesia is unknown. Several studies have demonstrated that timed-intermittent boluses, in combination with patient-controlled epidural analgesia (PCEA), provide superior

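### Time to first redose: delivery is a competing event, so a Kaplan-Meier curve or median that censors at delivery overstates redosing if read as the share or timing of women redosed

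*Combined protocol and SAP*

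**What the plan says.** The hypothesis under Aim 1 (section 1.0) is that the 300 mL/h group "will have a longer duration of adequate analgesia (time to first manual redose request"), so the time to first redose is what the aim means by duration.

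Section 5.0, Data evaluation, makes a different quantity primary: "The primary outcome will be the proportion of patients requiring supplemental manual boluses of local anesthetic". It then lists further outcomes: "time to first PCEA request, time to first supplemental manual bolus, and motor block at 10 cm cervical dilation will be evaluated".

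For the time outcomes the method is: "Time outcomes will be compared between groups using a Kaplan–Meier survival analysis technique with log rank test". Under the censoring rule, women who have a cesarean or who "do not request supplemental analgesia will be censored at the time of delivery".

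No cumulative-incidence or competing-risk method appears anywhere. The plan does not name a median, a Kaplan-Meier percentage or a Kaplan-Meier difference between arms as an output.

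**The concern.** Censoring normally means that the event could still happen but was not observed. Here every woman without a redose leaves follow-up by delivering, and after that a labor redose is impossible. Kaplan-Meier nevertheless gives her the later redose risk of women still in labor. One minus the curve (1-KM) then describes a labor that never ends, and only under the further assumption that delivery time is unrelated to redose need. The plan neither states that target nor justifies the assumption.

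What is at stake is how the only duration analysis for Aim 1 is read. The same report would hold a crude proportion redosed and a curve for the same event that ends well above it. It could also show a median duration of analgesia for an arm in which about 30% of women are ever redosed.

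**Working it through.** **Inputs from the documents.** Section 3.0 (sample size): redose proportions 0.50 (100 mL/h) and 0.30 (300 mL/h), power 0.8, alpha 0.05, 106 per group. Section 3.0 (exclusions): delivery within 90 minutes is excluded, so follow-up exceeds 1.5 h. Section 5.0: the method and censoring rule above. No labor duration or redose timing is given, so these are assumed below.

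**The plan's own figure.** For two proportions, two-sided, with pooled variance under the null:

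n = [1.96 × √(2 × 0.4 × 0.6) + 0.842 × √(0.25 + 0.21)]² / 0.2² = 93.

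With continuity correction: (93/4) × [1 + √(1 + 4/(93 × 0.2))]² = 103, within 3% of the stated 106. The trial is sized on the crude proportion, so nothing below touches the sample size.

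**Share of women whose follow-up ends by delivery.** 1 − 0.50 = 50% and 1 − 0.30 = 70%, or about 53 and 74 women of 106.

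**Direction.** At a time with d redoses among n women at risk:
- 1-KM rises by S_R(t−) × d/n, where S_R is the Kaplan-Meier redose-free curve with delivery censored.
- Cumulative incidence rises by S_R(t−) × S_D(t−) × d/n, where S_D is the matching curve for remaining undelivered.

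Since S_D ≤ 1, 1-KM is never below the cumulative incidence. It exceeds it once a redose follows another woman's redose-free delivery. With no other loss to follow-up, cumulative incidence is simply the number redosed by time t divided by all women, so it ends at the crude proportion.

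**Size, first set of assumptions.** Simulated time under analgesia is gamma, mean 8 h, SD 3 h, minimum 1.5 h. The redose hazard is solved so that 50% and 30% are redosed before delivery. Entries are percent, 1-KM v cumulative incidence; the last column is the subtraction, in points.

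| Redose hazard | Time | 100 mL/h | 300 mL/h | Arm difference |
|---|---|---|---|---|
| Constant | 6 h | 42.0 v 40.0 | 24.0 v 22.7 | 18.0 v 17.3 |
| Constant | 10 h | 59.7 v 48.4 | 36.6 v 28.7 | 23.1 v 19.7 |
| Constant | 12 h | 66.3 v 49.5 | 42.1 v 29.5 | 24.2 v 20.0 |
| Rising (Weibull shape 2) | 6 h | 34.0 v 31.0 | 17.7 v 16.0 | 16.3 v 15.0 |
| Rising (Weibull shape 2) | 10 h | 68.5 v 47.2 | 41.7 v 27.0 | 26.8 v 20.2 |

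With early-weighted redosing (Weibull shape 0.5) the 10 h gaps are about 6 and 4 points, which gives the lower ends of the ranges. At 10 h about 7-10% (100 mL/h) and 13-15% (300 mL/h) remain at risk, or roughly 7 to 16 women of 106.

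The Kaplan-Meier median in the 300 mL/h arm falls at 15.2 h (constant hazard, 1.0% at risk) or 11.3 h (rising hazard, 6.8% at risk). Only 28.5-29.9% have been redosed by then.

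**Shorter labors.** With a mean of 6 h and constant hazard, the 8 h figures are already 62.7 v 48.1 and 38.6 v 28.2.

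**Second set of assumptions.** Lognormal time to delivery (median 5, 7 or 9 h, log-SD 0.5) with Weibull redose times (shape 1.0 or 1.5). At 10 h the gap is about 8-35 points (50% arm) and 5-29 points (30% arm). In samples of 106, the final 1-KM averages 0.83-0.92 against 0.50, and 0.63-0.78 against 0.30. It exceeded the crude proportion in every sample (smallest gap 2.8 points). A finite Kaplan-Meier median appeared in about 70-94% of simulated 30% arms.

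**The case against.** **The plan promises a comparison, not these summaries.** This stands. The stated inference is the log-rank test, and no median or percentage is named. The error arises only when the curve is drawn and read as the share of women redosed. Curves and medians are, however, the usual output of such an analysis, and Aim 1 is worded as a duration.

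**The share redosed is already reported directly as the primary outcome.** This also stands. It means that the primary result is safe. It does not make the duration analysis right.

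**Kaplan-Meier may be the intended estimand.** How long analgesia lasts while labor continues is a fair question, and cumulative incidence mixes labor length into the answer. The reading needs delivery time to be unrelated to redose need, which the plan does not state. If that is the target, the curve should be labeled so.

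**The large gaps lie in the sparse tail.** This is correct for a mean of 8 h: through 6 h the gap is about 0-3 points. The Kaplan-Meier median of the 300 mL/h arm, where one exists, lies in that tail.

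**Stronger readings that the documents do not support.**
- *A reader might infer that the difference between arms will be inflated.* That depends on the scenario. At 10 h with a mean of 8 h, the excess is between about 2 and 7 points (21 v 19 when the hazard follows the fraction of labor completed, 21 v 20 with early-weighted redosing, 27 v 20 with a rising hazard). With a mean of 6 h and a rising hazard, the Kaplan-Meier difference has fallen below the true one by 14 h (about 14 or 15 v 20).
- *A reader might infer that the log-rank test or the primary analysis is invalid.* Neither is. The log-rank test compares redose rates among women still in labor, and the primary analysis uses no censoring.
- *A reader might infer the same error for time to first PCEA request.* The documents give no rate for it. If most women make a request, few are censored and the gap is small.

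**Conclusion.** The point holds in limited form. Delivery is a competing event for a labor redose, and by the plan's rates it ends follow-up for about half of one arm and 70% of the other. Any Kaplan-Meier curve or median taken as the share or timing of women redosed will overstate redosing and will not end at the primary proportion.

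The direction is algebraic. The size rests on assumed labor durations and hazard shapes: negligible early in labor, and several to about 20 points at 10 h under a mean of 8 h, where few women remain at risk. The calculations count any redose before a cesarean as an event; the censoring sentence can be read otherwise and should be clarified. This is a cheap and worthwhile improvement to a non-primary analysis and no threat to the trial's main conclusion.

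**What to change.** In section 5.0, Data evaluation, for time to first manual bolus:

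1. Present Aalen-Johansen cumulative incidence curves by arm, with delivery (vaginal or cesarean) without a prior redose as the competing event, and show numbers at risk.
2. Keep the log-rank test, described as a comparison of cause-specific hazards, and add the cause-specific hazard ratio with 95% CI.
3. Report a median only if the cumulative incidence reaches 50%.
4. If Kaplan-Meier curves are also shown, label them as redose-free time had labor continued, assuming delivery time is unrelated to redose need.
5. State that a redose before a cesarean counts as an event.

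The same approach may be used for time to first PCEA request, though no size of error is claimed there.

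Cost: a few sentences and a few lines of code. Redose times are already to be recorded, and delivery time is already needed for the censoring rule. The downside is a less familiar curve and possibly a smaller apparent absolute difference.

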The time to the first request for supplemental analgesia will be recorded on the study data sheet. The time, type and volume of local anesthetic used, and VAS scores before and 15 minutes after the redose will be recorded.

All other clinical management will be as per routine, and study participation will not interfere with anesthetic or obstetric care. Anesthesiologists will manage breakthrough pain in the usual manner (assessment of stage of labor and extend/density of neuraxial blockade, followed by the appropriate maneuver to reestablish adequate analgesia).

Following delivery, the patient will be asked to give one final VAS score and her overall satisfaction with labor using a 100 mm unmarked line (the left end labeled "not satisfied at all" and the right end labeled "extremely satisfied"). Mode of delivery, as well as the duration of the 1st and 2nd stage of labor will be recorded by study personnel.

Patient Controlled Epidural Analgesia (PCEA) pump utilization data will be downloaded from epidural pumps after delivery. This will include the time to first PCEA request, the number of PCEA demands, the number of times that PCEA boluses were delivered, the total amount of local anesthetic consumed.

4.0 Risks/Benefits:

Risks:

There is no risk of physical harm in this study. The study will not result in any change in management of the patient's pain other than the infusion rate of the timed-bolus epidural bolus, nor in any delay in diagnosis and treatment of pain.

Participants are at risk for loss of confidentiality. Strict measures will be in place to ensure that no loss of confidentiality occurs. All participants will be assigned a participant study number that will be used to identify them. One document will link the participant name to their participant number, and this will be kept in a password-protected computer in a locked office in the Prentice Women's Hospital. Only study investigators will have access to the study data.

Benefits:

Participants will derive no specific benefit from participation in this study; however, participation in this study will help us better understand the optimal rate for delivery of bolus doses of local anesthetic during maintenance of labor analgesia using timed-boluses.

Confidentiality:

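### Labor pain is scored as an undivided area under the VAS-time curve over a period that differs between women, so the score mixes pain with length of observation; dividing by observed time is a cheap improvement

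*Combined protocol and SAP*

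**What the plan says.** The pain score has one sentence, in section 5.0 Data Analysis, Data evaluation: "Labor pain will be calculated using the area under the VAS-time curve using the trapezium rule". It names no divisor, no start or end time, and no set of readings.

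The readings are described in section 3.0, Protocol specific methods:

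- A baseline VAS on a 100-mm line is taken before analgesia.
- An early reading follows: "Fifteen minutes following the intrathecal dose, a VAS score and a sensory level of analgesia will be obtained".
- Then: "The following information will be obtained hourly until complete cervical dilation (10 cm): VAS pain score, sensory level".
- Women who are redosed have extra readings: "VAS scores before and 15 minutes after the redose will be recorded".
- One last VAS is taken after delivery.

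Stage lengths are collected ("Mode of delivery, as well as the duration of the 1st and 2nd stage of labor will be recorded by study personnel") but are not linked to the pain score. The only test that could apply is the general one: "continuous data will be compared using a two-tailed t-test or Mann Whitney U test as appropriate". In the same paragraph, bupivacaine use is put on a per-hour basis.

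The VAS area is not listed as a primary or secondary outcome, nor among the additional outcomes.

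**The concern.** Women enter at any dilation up to 5 cm, in induced or spontaneous labor, and hourly VAS stops at 10 cm. The curve built from these readings therefore has a different length for each woman. An undivided area grows with that length, so a woman with mild pain and a long labor can score worse than one with twice the pain and a short labor.

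Two things are at stake. First, variation in labor length adds noise to a score meant to describe pain, which can cost power. Second, if the arms differed systematically in labor length, the score would differ even with the same pain at every moment.

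A smaller matter is which readings count. Redose readings exist only in women who had the primary event, so including or omitting them changes the score for those women alone.

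**Working it through.** **The plan's own figure.** The documents give no VAS mean, VAS SD or labor duration, so there is no pain figure to reproduce. The only computed figure is 106 per group for the primary outcome (50% v 30%, alpha 0.05, power 0.8; two-sided assumed). It is used here only as the arm size.

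- Uncorrected: n = [1.96·√(2·0.40·0.60) + 0.842·√(0.50·0.50 + 0.30·0.70)]² / 0.20² = 93.
- With continuity correction: (93/4)·[1 + √(1 + 4/(93·0.20))]² = 103, close to 106.

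**Step 1: what the area measures.** The trapezium rule gives A = Σ ½(v_i + v_{i+1})(t_{i+1} − t_i), which equals the time-weighted mean VAS times (t_last − t_first). For constant pain:

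- 15 mm × 12 h = 180 mm·h; 30 mm × 5 h = 150 mm·h. The order reverses.
- 20 mm for 2 h = 40 mm·h; 20 mm for 12 h = 240 mm·h. Divided by time, both are 20 mm.

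**Step 2: equal labor length in both arms.** Everything from here on rests on assumed distributions: mean VAS 30 mm with SD 17, time to 10 cm lognormal with mean 6 h and CV 0.4-0.6, and pain unrelated to duration. Each setting uses 106 per arm, a two-sided Mann-Whitney test at 0.05, and 4,000 simulated trials for power.

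With no pain difference, both scores reject in about 4-6% of trials. Chance imbalance in labor length is already inside that 5%.

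Power for mean VAS 30 v 23:

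| Assumed shape of pain | Undivided | Divided |
|---|---|---|
| Gamma, SD 17 | 0.82-0.90 | 0.94-0.95 |
| Truncated normal, SD 17 | 0.76-0.83 | 0.90-0.91 |
| Gamma, constant CV | 0.63-0.75 | 0.89 |

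The loss runs from 5 points (0.948 − 0.897) to 26 points (0.891 − 0.630).

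The independence assumption matters. On the log scale, Var(log A) = σ_P² + σ_T² + 2ρσ_Pσ_T, where P is mean pain, T is duration and ρ is their correlation. A positive ρ makes the loss larger; a negative ρ makes it smaller, and ρ = −σ_T/(2σ_P) cancels the added variance.

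**Step 3: hypothetical, bolus rate shortens labor and pain is unchanged.**

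- Flat pain, labor 10% / 15% shorter in one arm: the undivided area rejects in roughly 15-21% / 26-43% of trials. The range reflects the model; the upper end comes from modelling the hourly reading grid. The divided score stays near 5%.
- Pain rising 3-5 mm per clock hour: undivided 19-36% / 41-68%; divided 8-13% / 10-22%. Division helps but is not a full cure.

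The second case is worth showing because section 2.0 says: "Pain signals from the late first state and second stage of labor also arise from the vaginal and perineum".

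**Step 4: which readings enter.** Take an invented woman with VAS 10 at 0.25 h and 20 at each hour from 1 to 6 h.

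- Area = ½(10 + 20)·0.75 + 20·5 = 111.25 mm·h; divided by 5.75 h, 19.3 mm.
- Add a redose pair, 60 at 3.5 h and 10 at 3.75 h. The interval from 3 to 4 h changes from 20 to 20 + 8.75 + 3.75 = 32.5 mm·h.
- New area = 123.75 mm·h, 11% higher; divided, 21.5 mm.

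**The case against.** **Cumulative pain is a legitimate quantity.** If one arm's labor were shorter, its total pain would truly be lower. This stands: an undivided area is not an error in itself. But the plan calls the score labor pain and nowhere says that cumulative burden is the target, while the same paragraph standardizes drug use for time.

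**The authors may have meant a time-averaged area.** Possibly. The text is silent, and one clause would settle it.

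**Randomization balances labor length.** It does on average. A reader might infer that a chance imbalance produces a false pain difference beyond the nominal rate. It does not: such imbalance is already counted in the 5%.

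**The inflated rejection rates are hypothetical.** This stands too. A reader might infer that the plan's pain comparison is biased. That would need bolus rate to change the time to 10 cm, and no passage states or hypothesizes this.

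**The length of the curve is not fixed by the documents.** Correct. Time to 10 cm is the evident end because hourly VAS stops there. Baseline, redose and post-delivery readings are neither included nor excluded, and the censoring sentence covers the time outcomes, not the VAS curve of a woman with a cesarean before 10 cm.

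**The measure is unlisted, so the remedy should be light.** Accepted. Naming the readings and dividing by time is enough.

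**Conclusion.** The point holds as a minor, nearly free improvement. As written, the score is roughly mean pain times observed time, and nothing in the plan standardizes it.

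With no effect of bolus rate on labor length, type I error is kept. The cost is then power: about 0.82-0.90 against 0.94-0.95 in the gamma SD 17 setting, with a larger loss under the constant-CV shape. These figures depend on assumed VAS and duration distributions and on pain being unrelated to duration. The documents supply none of these, so the size is illustrative; the dependence of the area on time is arithmetic.

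The documents do not support reading this as a threat to the trial's main result. The primary outcome is the proportion needing a manual bolus; that outcome, the listed secondary outcomes and the 106 per group do not use the VAS area.

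**What to change.** In section 5.0, Data evaluation, state that:

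1. The area uses the 15-minute and hourly VAS readings up to 10 cm, or up to the last reading before a cesarean that precedes 10 cm.
2. It is divided by the time from the first to the last reading used, giving a time-weighted mean VAS in mm, and this is compared between arms with the test already planned for continuous data.
3. Baseline, redose and post-delivery VAS are reported separately.
4. First-stage duration is reported by arm beside the pain result, because division does not fully remove dependence on duration if pain rises with clock time.

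The undivided area may stay as a descriptive figure for cumulative pain.

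The cost is two or three sentences and one division per woman. No new data are needed: the VAS readings and stage durations are already to be collected. The downsides are that the main pain score no longer reads as cumulative pain, and that breakthrough pain recorded only at a redose appears beside the score rather than in it.
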